#### **5.5.10.2. Sensitivity Analysis for Primary Outcome**

Several types of sensitivity analyses are planned to assess the robustness of deviations from the assumptions of primary analysis including the target population, missing data assumption, and normality assumption and the influence of slight change in the definition of episodic migraine prevention.

##### **Target population Assumption**

Sensitivity analyses will be performed using different target population. They are implemented by repeating the primary analysis using PPS instead of ITT. Per protocol set excludes patients who hit criteria of important protocol deviation which would affect the primary efficacy analysis.

##### **Missing Data Assumption**

Sensitivity analyses will be performed to assess the robustness of the primary analysis conclusions to deviations from MAR assumption. The approach for these analyses is to vary the assumptions of missing data for the primary analysis in a systematic way. Basically, the method will be to predict the missing outcomes and then add values ( $\Delta_{120}, \Delta_{240}, \Delta_P$ ) to the predictions in the LY2951742 120 mg/month, LY2951742 240 mg/month, and placebo treatment groups respectively, consistent with the sensitivity approach suggested in Permutt (2015). This procedure will be repeated multiple times for different values of ( $\Delta_{120}, \Delta_{240}, \Delta_P$ ) using the following steps:

- 1) Predict the missing outcomes for each treatment via multiple imputation based on observed primary endpoint and baseline values. Such imputation will be carried out using a Markov Chain Monte Carlo method with a Jeffreys prior via SAS® PROC MI. Thirty (30) such imputations will be created.
- 2) Add the corresponding  $\Delta$  value (i.e.,  $\Delta_{120}, \Delta_{240}$ , or  $\Delta_P$ ) to the imputed values based on the patient treatment group.
- 3) Conduct the primary analysis separately for each of the 30 imputations.
- 4) Combine the results of these analyses using Rubin's combining rules, as implemented in SAS® PROC MI ANALYZE.

The above steps will be repeated multiple times for different values of  $(\Delta_{120}, \Delta_{240}, \Delta_P)$  with  $\Delta_P$  ranging from (0, twice the absolute value of the mean value seen for placebo in the primary analysis) and both  $\Delta_{120}$  and  $\Delta_{240}$  ranging from  $(\Delta_P, \Delta_P + \text{absolute value of the biggest mean treatment difference seen within the primary analysis})$ . For example, if the overall mean change from baseline for placebo is -3.6 and the maximum overall treatment difference is -1.5, then  $\Delta_P$  would range from (0, 7.2) and  $\Delta_{120}$  and  $\Delta_{240}$  would range from  $(\Delta_P, \Delta_P + 1.5)$ .

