**Figure CGAN.5.1. Study I5Q-JE-CGAN protocol design.**

### 5.2. Determination of Sample Size

The study will enroll approximately 451 patients. Eligible patients will be randomized in blinded fashion in a 2:1:1 ratio to placebo (target of 225 patients), galcanezumab 120 mg/month (target of 113 patients), or 240 mg/month (target of 113 patients). With the assumption of a 15% discontinuation rate and an effect size of 0.36, it is estimated that this sample size will provide approximately 88% power that at least 1 dose of galcanezumab will separate from placebo at a two-sided significance level of 0.05 based on simulations using the Dunnett's test (Dunnett 1955). Assumptions in the simulations were based on the assumptions for global Phase 3 studies, with adjustment to reflect less dropout and less variability in a more homogenous Japanese study.

Approximately 902 patients may be screened to ensure randomization of 451 patients, with an estimated 383 patients completing the study.

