For the 4 months of the post-treatment period, the monthly interval will be derived as below. Firstly, the 2-month visit interval will be split into two one-month periods for efficacy measures. If the number of days between two visits (visit x + 1 date - visit x date + 1) is even, the first half will be in the first one-month period and the second half will be in the second one-month period. If the number of days between two visits is odd, then the days will be split similarly, but the first one-month period will have one day more than the second one-month period. Secondly, after the two-month visit intervals are split into two one-month periods, the monthly data will be derived in the same way for each one-month period as for treatment phase. For patients who discontinued early during the post-treatment phase, if the date of discontinuation is within 30 days of previous visit date, all data between the previous visit date and the discontinuation date will go to one monthly period; if the date of discontinuation is more than 30 days of the previous

visit date, then the first 30 days will be the first monthly period, and the rest will be considered as part of the second monthly period.

This approach to missing ePRO diary data assumes that the rate of migraine headaches per day is the same for days with missing and non-missing ePRO diary days, and it is missing at random (MAR). The same approach will also be applied to secondary and exploratory efficacy measures that are derived from ePRO data.

Example 1: A patient has 64 days between Visit 13 and Visit 14. He completes the study on Visit 14. Then he has

- 1st half month = ePRO diary data from day 1 to day 32
- 2nd half month = ePRO diary data from day 33 to day 64.

Example 2: A patient has 64 days between Visit 13 and Visit 14. He discontinues the study on Visit 14 (i.e., disposition is not marked as completed). Then he has

- 1st half month = ePRO diary data from day 1 to day 30
- 2nd half month = ePRO diary data from day 31 to day 64.

Example 3: A patient has 70 days between Visit 13 and Visit 14 (outside of visit allowance). He completes the study on Visit 14. Then all data will be captured and he has

- 1st half month = ePRO diary data from day 1 to day 35
- 2nd half month = ePRO diary data from day 36 to day 70.

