Example 4: A patient has 70 days between Visit 13 and Visit 14 (outside of visit allowance). He discontinues the study on Visit 14 (i.e., disposition is not marked as completed). Then all data will be captured and he has

- 1st half month = ePRO diary data from day 1 to day 30
- 2nd half month = ePRO diary data from day 31 to day 70.

Example 5: A patient has 35 days between Visit 13 and Visit 14. He discontinues the study on Visit 14 (i.e., disposition is not marked as completed). Then he has

- 1st half month = ePRO diary data from day 1 to day 30
- 2nd half month = ePRO diary data from day 31 to day 35.

Example 6: A patient has 14 days between Visit 13 and Visit 14. He discontinues the study on Visit 14 (i.e., disposition is not marked as completed). Then he has

- 1st half month = ePRO diary data from day 1 to day 14
- 2nd half month = No ePRO diary data

Example 7: A patient has 14 days between Visit 5 and Visit 6. He discontinues the study on Visit 6. Then he has

- Month 2= ePRO diary data from day 1 to day 14

Additionally, if the compliance rate for each monthly interval is  $\leq 50\%$ , then all endpoints to be derived from the ePRO diary data for that one-month period will be considered missing. For the post-treatment phase, the derived one-month periods (resulting from splitting two-month visit interval) will be treated similarly. For a patient who discontinued early in the double-blind treatment phase or post-treatment phase, the compliance rate for the last month of that study period will be calculated with the denominator of the maximum of 30 and the total number of calendar days in that month, i.e.,  $\max(30, \text{the total number of calendar days in that month})$ . For the rest of months and the period, the compliance rate will be calculated as described in Section 5.5.7.

In the Example 7 above, diary compliance rate for Month 2 is less than 50% even if he has no missing diary for 14 days between Visit 5 and Visit 6. Note that he discontinues and the denominator is  $\max(30, 14) = 30$ . Hence, diary compliance rate =  $14/30 * 100 < 50\%$ . Hence Month 2 diary data is considered as missing.

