### Normality Assumption

To assess the robustness of the MMRM results to deviations from normality assumption, a sensitivity analysis for the raw number of migraine headache days (the total number of migraine headache days for each interval without normalization to 30-day period) will be conducted with a repeated measures negative binomial regression analysis fitted with SAS PROC GLIMMIX. The model will include treatment, month, and treatment-by-month interaction, as well as the continuous fixed covariates of baseline number of monthly migraine headache days and baseline-by-month interaction, log (number of compliant calendar days within each month/30) as the offset in the model. In case of non-convergence, baseline-by-month interaction may be excluded from the model.

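### The planned delta analysis shifts only months scored as missing; missed diary days inside scored months keep the missing-at-random assumption in every planned sensitivity analysis of the primary endpoint

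*SAP*

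**What the plan says.** SAP 5.4.1 builds each monthly migraine headache day count by multiplying the recorded count by 30/x, where x is the number of non-missing diary days. It gives the assumption openly: "This approach to missing ePRO diary data assumes that the rate of migraine headaches per day is the same for days with missing and non-missing" diary days, and it calls this MAR. If compliance in a month is 50% or less, "then all endpoints to be derived from the ePRO diary data for that one-month period will be considered missing". For the last month of a patient who discontinues early, compliance uses the larger of 30 and the calendar days as denominator, so that month is still scored if more than half is recorded.

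SAP 5.5.10.2 (Missing Data Assumption) says the delta analysis assesses robustness to departures from MAR. Step 1 is to "Predict the missing outcomes for each treatment via multiple imputation based on observed primary endpoint and baseline values". Step 2 adds an arm-specific delta to the imputed values. In the SAP's example the placebo delta runs from 0 to 7.2, and each active delta from the placebo delta to 1.5 above it.

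The remaining primary sensitivity analyses in 5.5.10.2 are the per-protocol set, Criteria C, LOCF ANCOVA, the IWRS-based baseline and a negative binomial model. The last uses unscaled counts with the log of compliant days over 30 "as the offset in the model".

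**The concern.** The primary endpoint rests on two MAR assumptions. One concerns missing months and is handled by the MMRM. The other concerns missed days inside scored months and is handled by 30/x scaling. The delta analysis varies only the first. In a 30-day month with 16 diaries, 14 days (47%) are extrapolated, yet no delta is applied.

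The same gap lets some post-discontinuation days through. In the SAP's Example 7 a patient stops after 14 recorded days; 14/30 is below 50%, so the month is missing and would be imputed and shifted. A patient who stops after 16 recorded days has 16/30 = 53%. That month is scaled by 30/16, and its 14 unrecorded days receive no delta. Crossing the 50% line takes the stress from full to none.

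At stake is the robustness statement. If diary skipping is related to migraine, and especially if that relation differs by arm, the delta analysis could report robustness to MAR departures after stressing only part of the missing data.

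**Working it through.** **Which assumption each primary sensitivity analysis uses for missed days**
- Delta analysis, per-protocol set, Criteria C, LOCF ANCOVA and IWRS baseline: 30/x-scaled monthly values.
- Negative binomial: an offset of recorded days, which is the same equal-rate assumption.
- Migraine attacks (5.5.1.2) carry the previous day's status forward, and weekly Month 1 counts (5.4.1) treat a missing day as migraine-free. Neither is a sensitivity analysis of the primary endpoint.

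**The plan's own figures (SAP 5.2)**
- Inputs: 225/113/113 patients, "With the assumption of a 15% discontinuation rate and an effect size of 0.36".
- Completers: 451 × 0.85 = 383.35; the SAP says 383.
- Two-sided 0.05 Dunnett test, normal approximation, 191/96/96 completers: critical value 2.226; noncentrality 0.36 / √(1/191 + 1/96) = 2.877; power for at least one dose 0.896. The SAP gives "approximately 88% power that at least 1 dose of galcanezumab will separate from placebo". The figures agree within 2 points, so 15% is used below as the plan's dropout input.

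**Share of missing diary days that gets no delta (illustration)**

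Assumptions not in the documents: all 15% dropout falls in the 6-month phase and is spread evenly, so a dropout loses half the phase on average; on-treatment compliance c is 80% to 95%. The 80% in protocol inclusion criterion [5] is a baseline entry rule, not an expected on-treatment value.

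- Days lost to dropout: 0.15 × 0.5 = 7.5% of patient-days.
- Missed days in scored months: 0.925 × (1 − c).
- Share = missed in scored months / (missed in scored months + 7.5%).
- Shift in the treatment difference at a 1.5-day gap, equal missingness by arm: 1.5 × 0.075 = 0.11 day as planned; 1.5 × (0.075 + missed in scored months) if these days are included.

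| c | Missed in scored months | Share unshifted | Shift with missed days included |
|---|---|---|---|
| 95% | 4.6% | 38% | 0.18 |
| 90% | 9.3% | 55% | 0.25 |
| 85% | 13.9% | 65% | 0.32 |
| 80% | 18.5% | 71% | 0.39 |

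At c = 98% the share is 1.85 / 9.35 = 20%.

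**How far the share depends on the assumptions**
- The simple formula ignores the 50% rule. A day-level simulation that applies it (15% dropout, c from 95% to 80%) gives 41% to 72% if days are missed independently, 40% to 63% with moderate clustering, and 35% to 50% with strong clustering. Clustering lowers the share because more poor months fall to 50% or below and are then shifted.
- Simple formula, c from 95% to 80%: dropout of 10% gives 49% to 79%, and 5% gives 66% to 89%. Returning to 15% dropout, a loss of a quarter of the phase per dropout gives 56% to 84%, and three quarters gives 28% to 61%.
- Over the whole grid (dropout 5% to 15%, a quarter to all of the phase lost, c 80% to 98%) the share runs from about 10% to 94%.

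**Unequal missingness by arm**

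With an assumed 18% dropout on active and 12% on placebo, at the top of the example grid (active delta 7.2 + 1.5 = 8.7), the planned shift is 0.09 × 8.7 − 0.06 × 7.2 = 0.35 day.

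**Check of the remedy**

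Take r migraine headache days on x recorded days out of E expected. If the daily rate on missed days is higher by delta/30, the 30-day value is (30/E) × [r + (E − x)(r/x + delta/30)] = 30r/x + delta × (E − x)/E. The scaled count already holds the MAR part, so only delta × missed/expected is added.

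**The case against.** The strongest reply is that this matters little for superiority. If both arms skip bad days to the same degree, both counts are understated and the difference usually shrinks. For example (assumed values), true means of 4.9 and 3.4 with 20% of migraine days and 10% of other days skipped give about 4.4 and 3.05, a difference of about 1.4 rather than 1.5. A bias in favour of the drug needs skipping that differs by arm, in a double-blind trial. SAP 5.5.7 also plans treatment comparisons of diary compliance by month and overall. All this stands, with one limit: those comparisons can show different skipping rates, but not whether skipped days are worse days.

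The reply also questions the remedy. A delta chosen for missing months need not suit isolated missed days in patients still on treatment, a fixed shift adds no day-level imputation uncertainty, and the baseline count, scaled in the same way, is left alone. These points argue for a supplementary version with its own delta, not for replacing step 2.

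A reader might infer several stronger things that the documents do not support:
- That only empty months are shifted. Months with some diaries but compliance of 50% or less are also set to missing and receive delta.
- That the SAP never treats missed days differently. It does so for migraine attacks and weekly Month 1 counts.
- That 38% to 71% describes this trial. It comes from assumed compliance and an assumed dropout pattern; the 383 are also described as completing the study, not explicitly the 6-month phase.
- That 0.11 day is the most the planned analysis can move the difference. That holds only with equal missingness by arm; the 18%/12% example gives 0.35.

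**Conclusion.** The structural point holds on the SAP's own text. Delta reaches only months scored as missing (compliance of 50% or less, or after dropout). Missed days inside scored months, including the unrecorded days of a discontinuer's last month when more than half is recorded, stay under the equal-rate assumption in every planned sensitivity analysis of the primary endpoint.

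The size cannot be fixed from the documents. The 38% to 71% share and the shifts of 0.11 against 0.18 to 0.39 day rest on 15% even dropout, 80% to 95% compliance, a 1.5-day gap and, for the shifts, equal missingness by arm; arm-differential missingness would change both shifts. A share of missing days is not a bias, and nothing here shows that the primary result is biased. The primary test is untouched. This is an improvement worth considering to one sensitivity analysis, or else a limit on what that analysis may be said to show.

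**What to change.** Keep the planned delta analysis and add a second version. After the imputation in step 1, add delta to the imputed months as now, and also add delta × (missed diary days / expected diary days) to each scored post-baseline month, by arm. For a discontinuer's last month use the larger of 30 and the calendar days as the denominator, so that the 14 unrecorded days in the 16-day example receive 14/30 of delta. The delta for missed days may be set separately from the delta for missing months. The 30 imputations, the model and Rubin's rules stay the same.

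If the second version is not added, word the robustness conclusion so that it covers missing months only.

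The cost is one derived variable, since diary days are already counted for 30/x and for compliance, plus one more set of runs. The downside is that the stress is larger under the illustrated assumptions, so the robustness result may be less favourable.

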When the unstructured covariance matrix is not utilized, the sandwich estimator (Diggle and Kenward 1994) will be used to estimate the standard errors of the fixed effects parameters. The sandwich estimator is implemented by specifying the EMPIRICAL option in SAS®. When the sandwich estimator is utilized, the Kenward-Roger approximation for denominator degrees of freedom cannot be used. Instead, the denominator degrees of freedom will be partitioned into between-subject and within-subject portions by the DDFM=BETWITHIN (DDFM=BW) option in SAS®. If the model is still non-convergence, then baseline-by-month interaction may be excluded from the model.

The primary endpoint of this study for each LY2951742 dose arm compared with placebo will be estimated as the main effect of treatment from the MMRM analysis during the 6-month treatment phase. This provides the average treatment effect across 6 months of double-blind treatment phase. The repeated-measures analysis will include data from all 3 treatment groups. The Type I error rate for the study will be controlled at a 2-sided 0.05 level (equivalently, one-sided 0.025 level). For the multiplicity adjusted p-value calculation for the primary endpoint, the pairwise treatment effect comparisons of each dose of LY2951742 versus placebo will be conducted using the Step-down version of Dunnett' s procedure.

To implement the multiplicity adjustment, SAS® PROC GLIMMIX (with dist=normal option and residual option) will be used with the "adjust=dunnett stepdown" option. When the model is

fit with unstructured covariance, “adjust=dunnett stepdown ADJDFE=ROW” option will be used to adjust denominator degrees of freedom. The adjusted p-values will be reported for both LY arms (control arm is placebo).

The primary analysis will be also performed without multiplicity adjustment by SAS® PROC MIXED. This is mainly to show point estimators at each month and associated 95% confidence intervals.

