### ANCOVA

Using LOCF imputation, the primary analysis is conducted with ANCOVA (without multiplicity adjustment) described in Section 5.5.1.1.

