#### Baseline definition by IWRS based eligibility date

Instead of using ePRO eligibility date, the one by IWRS will be used for the primary analysis without multiplicity adjustment (by PROC MIXED).

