### 5.5.10.3. Secondary and Exploratory Efficacy Analyses

Table CGAN. 5.5 summarizes planned efficacy analyses for Study Period III, Study Period III/IV, and Study Period IV. All response rates are derived from migraine headache days unless otherwise specified. There will be no multiplicity adjustment for statistical test except for the primary efficacy analysis.

If analysis results would be considered less informative, then such results may not be provided in CSR. For example, the change from baseline analysis for number of migraine headache days with triptan use, if baseline values (see Section 5.5.4) are less than 1 day for at least one of the arms, then these analysis may not be provided in CSR because the improvement (change from baseline) is difficult to evaluate.

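### Does the delta grid for the primary result need a tipping search beyond its cap and a named significance limit?

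*SAP*

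**What the plan says.** SAP 5.5.10.2 (Missing Data Assumption) creates 30 imputations and adds a delta to the imputed values by treatment group. Step 3 reads "Conduct the primary analysis separately for each of the 30 imputations", and the results are then combined by Rubin's rules. The placebo delta runs from 0 to twice the absolute placebo mean change. Both active deltas run from the placebo delta up to that delta plus the "absolute value of the biggest mean treatment difference seen within the primary analysis". The worked example is "if the overall mean change from baseline for placebo is -3.6 and the maximum overall treatment difference is -1.5", which gives a placebo delta of 0 to 7.2 and an active excess of 0 to 1.5.

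SAP 5.5.10.1 describes two runs of the primary model. One uses step-down Dunnett: "The adjusted p-values will be reported for both LY arms (control arm is placebo". The other is plain: "The primary analysis will be also performed without multiplicity adjustment by" PROC MIXED. Two neighbouring sensitivity checks name their limit. For ANCOVA: "Using LOCF imputation, the primary analysis is conducted with ANCOVA (without multiplicity adjustment". For the IWRS baseline: "the one by IWRS will be used for the primary analysis without multiplicity adjustment (by PROC MIXED". The delta check names none. SAP 5.5.1 sets two-sided 0.05 as the default level, and SAP 5.5.10.3 adds "There will be no multiplicity adjustment for statistical test except for the primary efficacy analysis".

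**The concern.** Two things look incomplete. First, if every grid point stays significant, the plan does not search further, so the reader learns only that the tipping delta lies beyond the cap. Two trials that both pass could differ several-fold in how far beyond. Second, step 3 refers to an analysis that exists in an adjusted and an unadjusted form. Rubin's rules pool estimates and standard errors, so an adjusted p-value would have to be formed after pooling, and no method for that is given. If a grid result fell between the unadjusted limit (1.96) and the Dunnett limit (2.23), the same output would count as kept on one reading and lost on the other. This is the SAP's only delta-based check of the primary result.

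**Working it through.** **Inputs.** From SAP 5.2: 225/113/113 patients, effect size 0.36, 15% discontinuation, two-sided 0.05, about 88% power, 383 completers. From SAP 5.5.10.2: placebo change -3.6, difference -1.5, and the grid above. Assumed here: dropout timing, missingness unrelated to outcome, equal monthly correlation of 0.3 to 0.7, and the same dropout in both active arms.

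**Design figure.** 451 × 0.85 = 383. With 191/96/96 completers, expected z = 0.36 × √(191 × 96 / 287) = 2.88. The two-sided Dunnett first-step limit for two comparisons with correlation 113/338 = 0.334 is 2.226. Power for at least one dose is then 89.6% (89.3% by a t-based simulation), within two points of the stated 88%.

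**Starting z.** The figure 2.88 discards every dropout's diary data. With all randomized patients, 0.36 × √(225 × 113 / 338) = 3.12. The MMRM keeps partial data. Its information gives 3.06 to 3.10 for equal 15% dropout spread over Months 1 to 5, and about 2.97 to 3.10 over the patterns below in which patients have post-baseline data.

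**Grid.** Let f and v be the mean and variance of a patient's share of missing months, dA and dP the deltas, and SE0 = 1.5 / starting z. Then

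z = (1.5 − dA·fA + dP·fP) / √(SE0² + dA²·vA/113 + dP²·vP/225).

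For 15% spread evenly after Months 1 to 5, f = 0.15 × 0.5 = 0.075 and v = 0.15 × 11/36 − 0.075² = 0.0402. At the far corner (dP 7.2, dA 8.7), starting from 2.88 (SE0 0.521), the numerator is 1.5 − 1.5 × 0.075 = 1.3875. The variance is 0.2717 + 0.0269 + 0.0093 = 0.3079, so z = 1.3875 / 0.555 = 2.50. Starting from 3.06 it is 2.64.

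Lowest z on the grid:

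| Active / placebo dropout | Start 2.88 | MMRM start | Start 3.12 |
|---|---|---|---|
| 15% / 15%, spread | 2.50 | 2.64–2.67 | 2.69 |
| 17% / 13%, spread | 2.21 | 2.32–2.35 | 2.37 |
| 15% / 10%, spread | 2.19 | 2.31–2.34 | 2.35 |
| 20% / 10%, spread | 1.77 | 1.86–1.89 | 1.90 |
| 10% / 20%, spread | 2.73 | 2.91–2.94 | 2.96 |
| 15% / 15%, all after Month 1 | 2.21 | 2.27–2.32 | 2.36 |
| 15% / 15%, no month observed | 2.05 | 2.05 | 2.17 |

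On the completers-only start, three of the first six rows fall between 1.96 and 2.23. On the MMRM start, none does. The last row does, but Table CGAN. 5.4 restricts the analysis to patients with a post-baseline observation, so those patients appear to be excluded.

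A simulation with 30 imputations, Rubin pooling, SD 1.5 / 0.36 = 4.17 and monthly correlation 0.6 agrees. Its lowest z is 2.74 for equal spread dropout, 2.31 for equal dropout all after Month 1, and 1.90 for 20% active against 10% placebo, spread.

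**Beyond the cap.** For equal 15% spread dropout and start 2.88, the tipping excess at the 2.226 limit is 4.3 days at placebo delta 0 and 3.2 days above a placebo delta of 7.2. At 1.96 it is 6.1 and 4.9 days. At the cap with placebo delta 0, active dropouts sit at −5.1 + 1.5 = −3.6, level with placebo dropouts. At an excess of 4.3 they would do 4.3 − 1.5 = 2.8 days worse than placebo dropouts.

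**The case for a change.** The strongest case for a change is that results which all pass the grid are not equally robust. For the same starting z of 2.88, equal dropout of 5%, 10% and 15% gives lowest grid values of 2.74, 2.61 and 2.50. The tipping excess above a placebo delta of 7.2 is nevertheless 10.1, 5.0 and 3.2 days. Individual grid points can also fall between the limits. In the simulation with 10% placebo and 20% active dropout, z at placebo delta 7.2 is 2.22, 2.06 and 1.90 for an active excess of 0, 0.75 and 1.5. Naming the limit would take one sentence, and the extra runs need no new data.

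The textual facts stand, and so do the intermediate grid points. They carry little weight, for three reasons. The spread from 10.1 to 3.2 days comes from the dropout share, which SAP 5.5.2 already tabulates by arm and visit. Because the pooled difference is close to linear in delta, with slope equal to the missing share, a reader can extrapolate from the planned output. The far values are also hard to interpret: an excess of 10.1 above 7.2 puts active dropouts at −5.1 + 17.3 = about 12 days above baseline, in patients enrolled with 4 to 14 migraine headache days (Protocol 6.1). Finally, in the 20% / 10% pattern the corner of the grid fails both limits, so the check reports fragility on either reading.

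**Conclusion.** No change follows. Stopping at a bound with a clear meaning, while the placebo delta runs to twice the placebo change, is a fair trade-off against an open-ended tipping search. The grid also does its job: it shows a loss of significance when active dropout clearly exceeds placebo dropout. The unnamed limit is a gap that analysts would fill sensibly. SAP 5.5.1 ties step-down Dunnett to the primary analysis, SAP 5.5.10.3 excludes adjustment elsewhere, and pooling by Rubin's rules leads naturally to unadjusted contrasts at two-sided 0.05. The choice matters mainly for the better dose, because the second step of the step-down procedure uses the unadjusted level anyway. SAP 5.5.10.2 presents the check as a test of robustness and attaches no pass or fail rule.

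Under the plan's own 15% discontinuation, equal across arms and spread over the months, the lowest grid z is about 2.5 to 2.7 and clears both limits. That range rests on the design effect size, the SAP's example deltas, missingness unrelated to outcome and the assumed timing. A smaller observed effect could bring a grid minimum between the limits. The pooled estimate and standard error would still let a reader apply either one. Reporting a tipping delta beside the missing share is a reasonable optional extra, but the planned check is sound without it.
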